3.2. Study Design

This protocol describes a randomized, double-blind, placebo-controlled multicenter study to evaluate the efficacy and safety of ENTO (Treatment Arm 1) vs. placebo (Treatment Arm 2) in combination with systemic corticosteroids for subjects with cGVHD.

A total of 100 eligible subjects will be randomized in a 1:1 manner to ENTO (Treatment Arm 1) or placebo-to-match (PTM) (Treatment Arm 2), and treated for 48 weeks during the blinded phase. Randomization will be stratified by the following 2 factors at the Baseline/Day 1 Visit:

Stratification Factor	Stratification Levels
Calcineurin inhibitor or MMF use	Yes vs. No
Disease severity as determined by the 2014 NIH Consensus cGVHD criteria	Moderate cGVHD: 
 • ≥ 1 organ with score = 2, or • ≥ 3 organs with score = 1, or • lung score = 1 Severe cGVHD: 
 • any organ score = 3 or • lung score ≥ 2

The final analysis for BORR is planned when all subjects have been on study for 24 weeks. All subjects will be followed up to 48 weeks for DOR evaluation. At the Week 48 visit, subjects who are still on investigational treatment (ENTO or PTM) and are eligible to remain on study will have the option to receive open-label extension (OLE) with ENTO. This OLE offers patients who are deriving a benefit from ENTO or those with no alternative treatments the opportunity for further therapy for a serious and life threatening disease.

An external multidisciplinary data monitoring committee (DMC) will review the progress of the study, perform interim reviews of safety data at regular intervals approximately every 3 months, and perform an interim review of efficacy data for futility when approximately 50% of subjects have been on study for 24 weeks, as described in the DMC Charter. The first DMC meeting will be conducted after the 20th subject has been on study for 4 weeks. The DMC will provide recommendations to Gilead as to whether the nature, frequency, and severity of adverse effects associated with study treatment warrant the early termination of the study in the best interests of the participants, whether the study should continue as planned, or the study should continue with modifications.

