8.5.5. Final Analysis

The final analysis for BORR is planned when all subjects have been on study for 24 weeks. Duration and quality of response will continue to be assessed up to 48 weeks.

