1.2. Study Design

This is a randomized, double-blind, placebo-controlled, multicenter study to evaluate the efficacy and safety of ENTO (Treatment Arm 1) vs. placebo (Treatment Arm 2) in combination with systemic corticosteroids in subjects with cGVHD. An interim analysis for futility is planned when approximately 50% of subjects have been on study for 24 weeks, or have discontinued the study before 24 weeks, or have achieved a response prior to reaching 24 weeks. The primary endpoint will be evaluated when all subjects complete 24 weeks of treatment. Duration and type of response (complete or partial) will be evaluated for up to 48 weeks of blinded treatment. After 48 weeks, subjects who are still on investigational treatment (ENTO or placebo-to-match [PTM]) and are eligible to remain on study will have the option to participate in an open-label extension (OLE) to receive ENTO and attend visits per the schedule of assessments ([Appendix 1](#)) for an additional 96 weeks. Subjects who complete the study through week 48 and do not wish to participate in the OLE will be required to return to the clinic after completion of study drug for a 30-Day Follow-up Visit. This OLE offers patients who are deriving a benefit from ENTO and have no alternative treatments the opportunity for further therapy for a serious and life threatening disease.

Figure 1. Study Schema

- a Following the Baseline/ Day 1 visit subjects will return to the clinic for visits at weeks 2, 4, 8, 12, 16, 20, 24, 30, 36, 42 and 48.
- b For subjects receiving tacrolimus, cyclosporine or MMF the blood levels of tacrolimus, cyclosporine or the active metabolite of MMF (MPA) will be monitored at baseline/Day 1 (prior to starting ENTO or PTM), on day 2 or day 3 and day 6 or day 7 after initiating ENTO or PTM, and at the end of week 2 and Week 50 study visit. Beyond these time points, concentration monitoring for tacrolimus, cyclosporine and MPA should follow the treating institutions protocol and therapeutic range for monitoring these medicines
- c Subjects who complete the study through week 48 and do not wish to continue to participate in the OLE phase of the trial will be required to return to the clinic 30 days after the completion of study drug for a 30-Day Follow-up visit
- d After Week 48, all subjects will have the option to receive OLE for an additional 96 weeks. Subjects will attend visits at Weeks: 50, 52, 56, 60, 64, 72 and every 12 weeks thereafter.

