3.1.2. Safety Analysis Set

The Safety Analysis Set includes data from all subjects who received at least 1 dose of study drug, with treatment assignments designated according to actual treatment received. All data collected up to earlier of the last dose of study drug plus 30 days or first dose of OLE will be included in the safety summaries. The Safety Analysis Set will be used for analyses and summaries of exposure of study drug, corticosteroids, prior and concomitant medication, laboratory data, vital signs, and AEs.

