6.4. Secondary Efficacy Endpoints

6.4.1. Definition of Secondary Efficacy Endpoints

The key secondary endpoints are:

- Change from baseline in the skin domain of the LSS at 24 weeks
- Change from baseline in the mouth domain of the LSS at 24 weeks
- Change from baseline in the eyes domain of the LSS at 24 weeks
- Change from baseline in the total score of the LSS at 24 Weeks

Other secondary endpoints include:

- Duration of response, defined as the time from the documentation of BORR to the documentation of PD as defined in [Table 3](#). Note that a flare does *not* constitute an end to response. A sensitivity analysis for DOR could consider a flare does constitute an end to response.
- Proportion of subjects who ever achieve at least 50% reduction in systemic corticosteroid dose relative to baseline, where % reduction is calculated as (systemic corticosteroid dose at 24 weeks – baseline systemic corticosteroid dose) / baseline systemic corticosteroid dose.
- Proportion of subjects who initiate second-line therapy for cGVHD, defined as receiving any therapy besides systemic corticosteroids or study drug for the treatment of cGVHD. Inhaled and topical steroids are not considered second-line therapy.
- Failure-free survival (FFS), defined as the time from randomization to the earliest of first documentation of systemic therapy change, non-relapse mortality, or recurrent malignancy

- Safety and tolerability of ENTO

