6.4.2. Analysis Methods for Secondary Efficacy Endpoints

The key secondary endpoints will be analyzed using a two sample z-test at week 24.

Other secondary endpoints will be analyzed as follows:

DOR and FFS will be analyzed using the Kaplan-Meier (KM) method and stratified logrank test. Kaplan-Meier summary statistics (median, 95% CI for median, and 25th, 75th percentiles) and number and percentage of events will be presented by treatment group. A stratified Cox proportional hazards model will be used to estimate the hazard ratio and corresponding 95% CI. A KM survival plot will also be provided. Data for subjects who do not experience an event will be censored at the date of last visit. DOR will be analyzed only on subjects who responded.

Proportion of subjects with at least 50% reduction in systemic corticosteroid dose relative to baseline and proportion of subjects who initiated a second-line therapy for cGVHD will be analyzed similarly to the primary endpoint.

Line plot of change from baseline in each domain and total of LSS will be done.

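### FFS follow-up in SAP 6.4.2 is not cut at the first open-label dose, and the same sentence omits the 48-week limit that other sections set for DOR

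*SAP*

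**What the plan says.** SAP 6.4.2 analyses DOR and FFS by Kaplan-Meier, stratified log-rank test and stratified Cox model. Its only censoring rule is: "Data for subjects who do not experience an event will be censored at the date of last visit". Protocol 8.5.2 has the same rule. Neither mentions Week 48 or the first OLE dose.

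SAP 6.4.1 gives FFS no end point in time: it is "defined as the time from randomization to the earliest of first documentation of systemic therapy change, non-relapse mortality, or recurrent malignancy".

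After Week 48, subjects still on investigational treatment and eligible to remain on study "will have the option to participate in an open-label extension (OLE) to receive ENTO" for a further 96 weeks (SAP 1.2). Protocol 6.4 schedules visits to Week 144.

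For DOR there is a limit, stated outside the analysis section. SAP 1.2 says: "Duration and type of response (complete or partial) will be evaluated for up to 48 weeks of blinded treatment". Protocol 3.2 says: "All subjects will be followed up to 48 weeks for DOR evaluation", and Protocol 8.5.5 says: "Duration and quality of response will continue to be assessed up to 48 weeks".

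For safety, SAP 3.1.2 sets an explicit cut: "All data collected up to earlier of the last dose of study drug plus 30 days or first dose of OLE".

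**The concern.** From Week 48 an OLE subject takes ENTO whichever arm he or she was randomized to. SAP 3.2 keeps efficacy subjects in their randomized arm. If FFS follow-up runs to the last visit of any kind, part of the placebo curve describes ENTO treatment. Both arms then share one treatment, in a subset selected for still being on study drug. If ENTO has an effect, the hazard ratio is pulled toward 1 and the placebo Kaplan-Meier tail is mislabelled.

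The OLE also raises questions about what counts as an FFS event. Systemic therapy change is not defined further. The plan does not say whether starting open-label ENTO is such a change in a former placebo subject. Nor does it say whether a change made to meet the OLE time limit on co-administration with cyclosporine, tacrolimus or MMF (Protocol 5.4) is one. A cut at the first OLE dose removes both questions.

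**Working it through.** **1. The plan's own figures.** None is given for FFS or DOR. The sample-size figures in SAP 1.3 concern BORR and are not touched by this point. They reproduce: exact power of Fisher's test with 40 per arm, 50% against 80%, is 74.9% (stated 75%), and 80 / (1 − 0.20) = 100.

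**2. Can last visit mean an OLE visit?** I looked for any text that would exclude it.
- SAP 2.3 runs the final analysis after all follow-up or early-termination visits, so there is no data cut at Week 48.
- The visit windows in SAP 3.8.2, Table 1, are for the double-blind phase, but SAP 3.8.3 says a time-to-event analysis does not need one value per window. They do not truncate FFS.
- The restriction of tables to double-blind data covers adverse events (SAP 7.1.6), laboratory results (7.2.1) and weight and vital signs (7.3). Efficacy has no counterpart.
- The NCAA continues in the OLE (SAP Appendix 1), so efficacy data are collected there.

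For FFS nothing visible stops the clock at Week 48. For DOR the 48-week statements do, though not in the section that a programmer would follow.

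**3. How much could it matter?** The documents give no FFS rates, so this is an illustration on assumed inputs:
- exponential FFS, with placebo event-free proportion at Week 48 of S = 30%, 50% or 70%;
- placebo hazard h0 = −ln(S)/48 per week, and ENTO hazard h1 = 0.60 × h0;
- a share q of event-free subjects in each arm enters the OLE, has hazard h1 from then on, and is followed to Week 144; the rest are censored at Week 48;
- 200,000 simulated subjects per arm.

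Hand check at S = 50%: h0 = 0.693/48 = 0.01444 and h1 = 0.00866. Mean placebo time before Week 48 is (1 − 0.5)/0.01444 = 34.6 weeks. If all enter, mean OLE time is 0.5 × (1 − e^(−0.00866 × 96))/0.00866 = 32.6 weeks. The share on ENTO is 32.6/(34.6 + 32.6) = 48.5% (simulated 48.4%). If 5% enter, it is 1.63/(34.6 + 1.63) = 4.5% (simulated 4.5%).

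Hazard ratio without a cut, with the share of placebo-arm time on ENTO in brackets:

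| OLE entry q | S = 30% | S = 50% | S = 70% |
|---|---|---|---|
| 5% | 0.610 (2.7%) | 0.612 (4.5%) | 0.620 (6.3%) |
| 20% | 0.628 (9.8%) | 0.648 (15.8%) | 0.663 (21.3%) |
| 50% | 0.666 (21.7%) | 0.697 (32.1%) | 0.720 (40.4%) |
| 100% | 0.708 (35.3%) | 0.747 (48.4%) | 0.788 (57.6%) |

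With a cut at Week 48 the hazard ratio stays between 0.597 and 0.608 in every cell, which is 0.60 within simulation error.

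The illustration ignores dropout before Week 48 and takes OLE entry as random among event-free subjects. Actual entry is selective, and every OLE subject here could reach Week 144, which early termination makes unlikely.

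**The case against.** Analysing randomized groups over all follow-up is a recognised intent-to-treat choice, and the safety cut serves another purpose: attributing events to the drug being taken. That stands as a principle, so the safety rule alone does not prove the efficacy rule wrong. But the plan nowhere says that it wants a comparison of immediate with delayed ENTO, and its design text confines the comparison of response duration to blinded treatment.

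The consequence is also limited. SAP 3.5 drops formal comparisons after early termination, FFS lies outside the tested hierarchy in Protocol 8.5.2, and the SAP revision log describes OLE data as very sparse. Dilution also needs a true difference to dilute, and the trial stopped for lack of efficacy. All of this stands. It lowers the importance but does not settle the rule, because SAP 6.4.2 still specifies the Kaplan-Meier, log-rank and Cox outputs.

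A reader might infer three stronger things that the documents do not support:
- That DOR is equally unprotected. It is not; SAP 1.2 and Protocol 3.2 and 8.5.5 limit it to 48 weeks.
- That 96/144 = 67% of follow-up is open-label. That is the ceiling for one subject who completes the whole OLE, not a share of arm-level time or events.
- That placebo subjects did contribute ENTO time to FFS. They could, if event-free and enrolled in the OLE; the documents do not show how many were.

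**Conclusion.** The point holds for FFS: as written, event-free placebo subjects who enter the OLE carry open-label ENTO time and events into the placebo arm. For DOR it is an alignment matter between the censoring sentence and the 48-week limit stated elsewhere.

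The effect in this trial is probably small. If OLE entry was near the lowest assumed level (5%), a true hazard ratio of 0.60 would be reported as 0.61 to 0.62. Shifts to 0.71 to 0.79 need every event-free subject to enter and a full 96-week OLE. These values rest on the assumed event rates, an assumed true effect and an immediate change to the ENTO hazard. If there is no true effect, this model gives no dilution.

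SAP 6.6, on changes to the efficacy analyses, is redacted, so a truncation rule there cannot be excluded. This is a minor correction and bears on no confirmatory conclusion.

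**What to change.** In SAP 6.4.2, state that FFS and DOR are censored at the earlier of the last visit and the first OLE dose, and that events on or after the first OLE dose are not counted. For DOR, also apply the 48-week limit from SAP 1.2 and Protocol 3.2. If SAP 6.6 already contains such a rule, repeat it or refer to it in 6.4.2.

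The cost is one or two clauses and a small amount of follow-up after Week 48, which carries no ENTO-versus-placebo contrast. Because the OLE starts only after Week 48, the cut works much like a common administrative end date and adds little risk of informative censoring. Subjects who decline the OLE keep their 30-day follow-up visit for FFS, a minor asymmetry.

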
Proportion of subjects with at least 50% reduction in systemic corticosteroid dose relative to baseline and proportion of subjects who initiated second-line therapy for cGVHD will be analyzed similarly to the primary endpoint.

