1.3. Sample Size and Power

With 40 subjects per treatment group, there is 75% power to detect a 30% improvement in response rate at a 2-sided 0.05 significance level using Fisher’s exact test, assuming a placebo response rate of 50%. A total of 100 subjects (50 per treatment group) will be enrolled assuming a 20% dropout rate.

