3.6. Missing Data and Outliers

3.6.1. Missing Data

Missing data can have an impact upon the interpretation of the trial results. In general, values for missing data will not be imputed unless methods for handling missing data are specified. The handling of missing or incomplete dates is described in Section 7.1.5.2 for AE onset, in Section 6.3 for efficacy, in Section 7.4 for prior and concomitant medications, and in Section 7.1.5.2 for missing last dose date.

Values for missing safety laboratory data will not be imputed; however, a missing Baseline/Day 1 result will be replaced with a screening result, if available. If no pre-treatment safety laboratory value is available, the Baseline/Day 1 value will be assumed to be normal (ie, no grade) in the summary of graded laboratory abnormalities. Values for missing vital signs data will not be

imputed; however, a missing Baseline/Day 1 result will be replaced with a screening result, if available.

- If safety laboratory results for a subject are missing for any reason at a time point, the subject will be excluded from the calculation of summary statistics for that time point. If the subject is missing a pre-dose value, then the subject will be excluded from the calculation of summary statistics for the pre-dose value and the change from pre-dose values.

SAS code to calculate the LSS score and handle missing data are provided in [Appendix 6](#).

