6.3. Analysis of the Primary Efficacy Endpoint

The primary analysis for BORR will be performed in the ITT Analysis Set, which includes all subjects who were randomized. Response rate will be summarized by count and percent of subjects with each ordinal response (CR, PR, CR or PR, SD and PD). A stratified Cochran-Mantel-Haenszel (CMH) Chi-square test will be performed to compare BORR (CR + PR) between ENTO and placebo-to-match (PTM) by 24 weeks. The difference in response rates between treatment groups and the corresponding 95% CIs will be presented.

If the entire NIH questionnaire is missing, then the organ and subject level statuses are missing. Missing individual NIH domain scores, for example, skin score, will lead to missing status for skin domain. In such a case, the subject level status will be based on the remaining available domain statuses. This is equivalent to imputing the missing domain status as ND or NA.

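### Initiation of second-line therapy is analysed as a crude proportion with no time horizon, so incomplete follow-up understates the rate, shrinks a true difference and modestly favours the arm that loses more subjects from the study

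*SAP*

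**What the plan says.** SAP 6.4.1 defines the endpoint as "Proportion of subjects who initiate second-line therapy for cGVHD, defined as receiving any therapy besides systemic corticosteroids or study drug" given for cGVHD; inhaled and topical steroids do not count. No time point is attached. In the same section, the four Lee Symptom Scale endpoints and the steroid-reduction formula all name 24 weeks.

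For the analysis, SAP 6.4.2 says "proportion of subjects who initiated a second-line therapy for cGVHD will be analyzed similarly to the primary endpoint", and Protocol 8.5.2 has "proportion of subjects who initiated second-line therapy for cGVHD will be analyzed similarly to the primary endpoint". The primary analysis in SAP 6.3 sets the template: "The primary analysis for BORR will be performed in the ITT Analysis Set, which includes all subjects who were randomized", with a stratified CMH test and a difference with 95% CI, comparing response "between ENTO and placebo-to-match (PTM) by 24 weeks".

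The missing-data text in SAP 6.3 concerns the NIH questionnaire only. The general rule in SAP 3.6.1 is that "values for missing data will not be imputed unless methods for handling missing data are specified", and none is specified for second-line therapy. DOR and FFS, in the same SAP section 6.4.2, get Kaplan-Meier estimates with censoring at the last visit.

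On follow-up, SAP 1.3 says "A total of 100 subjects (50 per treatment group) will be enrolled assuming a 20% dropout rate". SAP 2.3 records that the sponsor ended the study early and that the final analysis follows each subject's follow-up or early-termination visit.

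**The concern.** The primary endpoint counts a favourable event, so scoring an unobserved outcome as no event works against the arm that loses subjects. Starting second-line therapy is an unfavourable event, so the same convention works in that arm's favour. A subject observed for 3 weeks and one observed for 48 weeks carry equal weight, and the first has had little chance to record the event.

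Three things are at stake: the reported rate in each arm, the size of any true difference, and fairness between arms if losses are unequal. The missing horizon adds to this, because the same data give quite different percentages at 24 weeks, at 48 weeks or over all follow-up. Safety data are cut at the first open-label dose (SAP 3.1.2), but no such cut is written for this endpoint.

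**Working it through.** **The plan's own figures.** The documents give no expected rate for second-line therapy. The one relevant figure is the enrolment target: 40/(1 − 0.20) = 50 per arm, 100 in total, which reproduces. The 20% is an overall dropout rate; no rate by arm is given. All event rates and arm-specific losses below are therefore assumptions.

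**Set-up.** Let q be the true risk by Week 48 and l = −ln(1 − q) the constant hazard, with 48 weeks as one unit of time. Subjects without a recorded event stay in the denominator as no.

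**1. Fraction d lost at a time uniform over 48 weeks, independent of the event.** Crude proportion = (1 − d)q + d(1 − q/l).
- q = 0.40: l = 0.5108 and 1 − q/l = 0.2169. With d = 0.20: 0.80 × 0.40 + 0.20 × 0.2169 = 0.363.
- q = 0.20: l = 0.2231 and 1 − q/l = 0.1037. With d = 0.20: 0.80 × 0.20 + 0.20 × 0.1037 = 0.181.
- A true 20-point difference appears as 36.3% − 18.1%, about 18 points.

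**2. Follow-up spread evenly over 4 to 48 weeks**, as staggered entry with early termination might produce. Crude proportion = 1 − [exp(−l/12) − exp(−l)]/(11l/12).
- q = 0.40: 1 − (0.9583 − 0.6000)/0.4683 = 0.235.
- q = 0.20: 1 − (0.9816 − 0.8000)/0.2045 = 0.112.
- The 20 points appear as about 12. The ratio barely moves (0.235/0.112 = 2.1, against 2.0).

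**3. No true effect, unequal loss.** With q = 0.40 in both arms, the formula in step 1 gives:
- d = 0.30: 0.70 × 0.40 + 0.30 × 0.2169 = 0.345.
- d = 0.10: 0.90 × 0.40 + 0.10 × 0.2169 = 0.382.
- The arm with more loss looks better by about 3.7 points.

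As a second model, let loss be exponential with m = −ln(1 − d). Then crude proportion = l/(l + m) × [1 − exp(−(l + m))]. For loss of 30% against 10%:

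| True risk, both arms | Crude, 10% loss | Crude, 30% loss | Difference (points) |
|---|---|---|---|
| 20% | 19.0% | 16.9% | −2.1 |
| 30% | 28.6% | 25.5% | −3.1 |
| 40% | 38.1% | 34.2% | −4.0 |
| 50% | 47.7% | 42.9% | −4.8 |

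(Differences are taken before rounding.) With 20% loss in both arms the difference is 0, although a true 30% shows as 27.1%.

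**4. Scale.** With 50 per arm and a rate near 36%, the standard error of the difference is √(2 × 0.36 × 0.64/50) = 0.096. The 3.7 points are therefore about 0.4 standard errors (3.7/9.6).

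**5. Horizon.** Under a constant hazard, a 30% risk at 24 weeks becomes 1 − 0.70² = 51% at 48 weeks.

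These calculations treat loss as independent of the event. Death is not modelled separately. For death, cumulative incidence does not create a failure; it displays death as a separate outcome beside second-line therapy.

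**The case against.** Much of the case on the other side stands.

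- **Limited inferential weight.** This is not a key secondary endpoint and lies outside the protocol's testing sequence. SAP 3.5 says that no formal comparisons will be made after the early termination. That stands, and it is why no new test should be required. SAP 6.3 and 6.4.2 still call for the proportions, their difference and its CI, however, and those figures carry the problem whether or not a p-value is attached.
- **FFS already uses time-to-event methods.** It counts systemic therapy change, non-relapse mortality and recurrent malignancy. This helps, but as a composite it does not isolate second-line therapy.
- **A 24-week reading is possible.** Analysis like the primary endpoint might be taken to import its 24 weeks. This is not written, and subjects lost before Week 24 would still be unaddressed.
- **The scoring of lost subjects is inferred.** No sentence says that they count as no. It follows from a denominator of all randomised subjects, an event counted only when recorded, and no imputation rule.
- **SAP 6.6 is redacted**, so it cannot be seen whether it addresses the point.
- **Censoring is not bias-free either.** Protocol 3.4 lists the need for disallowed cGVHD therapy as a reason to discontinue participation, so loss may be informative. This stands and shapes the fix.

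Two stronger readings are tempting but unsupported. A reader might infer that the arm with more toxicity-related stopping of study drug will look better. Protocol 6.5.2 asks subjects who stop drug early to attend visits through Week 48, and 6.5.1 asks that those starting second-line therapy be kept in the study. Stopping drug alone does not hide the event; death, withdrawal from the study or cut-off does. A reader might also infer serious contamination from placebo subjects taking ENTO in the open-label extension. The SAP revision log says that there are very few data from that phase.

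**Conclusion.** The point holds as a moderate weakness of a secondary analysis. With no horizon and no handling of incomplete follow-up, the planned proportion understates initiation of second-line therapy in both arms and shrinks a true difference. Under assumed rates of 40% and 20%, 20 points become about 18 at the planned 20% dropout, or about 12 with follow-up spread evenly over 4 to 48 weeks. Bias between arms when there is no true effect requires unequal loss from the study. It is about 2 to 5 points for an assumed 30% against 10%, well within sampling error at 50 per arm, and zero if loss and risk are equal. The documents report no imbalance between arms, so they do not show that ENTO is favoured. If subjects leave because they need disallowed therapy, the bias could be larger than these independent-loss figures.

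**What to change.** In SAP 6.4.1, state the horizon: Week 24, and Week 48 for the double-blind period. In SAP 6.4.2:

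- Report by arm the Aalen-Johansen cumulative incidence of second-line therapy with 95% CI at those times. Treat death as a competing event and show its curve alongside.
- Censor at the last date on which medication use was ascertained or at the first open-label dose, whichever is earlier.
- Keep the crude count as a descriptive line.
- Add a sensitivity analysis that counts death or withdrawal from the study as failure, because censoring may be informative.
- Use a stratified cause-specific log-rank test only if testing is retained, given SAP 3.5.

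The cost is SAP wording and one standard procedure; the medication start dates needed are already used in SAP 7.4.2. The downside is slightly more analysis work and wider intervals at late time points, where few subjects remain at risk.
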